## Introduction

Immunodeficiency of aging is manifested in terms of increased infections, autoimmune disorders, and cancers in geriatric population. Immunodeficiency is apparently a multi-factorial problem, where the loss of immunologic vigor in geriatric population plays a major role in the above-mentioned diseases. This has been substantiated with the reported age-dependent reduction of leukocyte qualitative functions in many studies (Fulop et al., 1985; Tortorella et al., 2002; Tortorella et al., 2006; Sansoni et al., 2008). Of particular interest was the reported age-dependent reduction of natural killer (NK) cells, which constitutes the primary defense line against malignant and virally-infected cells (Lotzova 1984; Moretta et al., 2002; Chretien et al., 2014; Ivarsson et al., 2014). Enhancing NK cell activity is therefore an essential therapeutic target in geriatric population.

Biobran/MGN-3 is defined by the Medicines and Healthcare products Regulatory Agency (MHRA) as a food supplement (McDermott, 2006). Biobran/MGN-3 is manufactured by hydrolyzing rice bran with the enzymatic extract of medicinal Shiitake mushrooms (Ghoneum and Jewett, 2000; McDermott, 2006). Enzyme hydrolysis of rice bran produces arabinoxylane, a hemi-cellulose compound, which constitutes the active ingredient of Biobran/MGN-3. Several studies demonstrated the potent immunomodulator effect of Biobran/MGN-3 (Ghoneum and Jewett, 2000; Ghoneum and Gollapudi, 2003; Badr El-Din et al., 2008; Ghoneum and Agrawal, 2011; Cholujova et al., 2013; Ghoneum et al., 2014). For example, earlier studies by Ghoneum have shown the superb capability of MGN-3 to enhance NK cell activity in human subjects aged 20-46 years (Ghoneum 1998). The induction of NK cell activity reached 2-3 folds of the baseline level after one month of supplementation. Biobran/MGN-3-induced upregulation of NK cell activity was associated with an increase in the granular content of NK cells. Other studies demonstrated that Biobran/MGN-3-induced NK cell activity was associated with increased Tumor Necrosis Factor (TNF- $\alpha$ , a cytokine involved in activating the immune system) and increased number of NK cells, T-cells and B-cells (Ghoneum and Jewett, 2000).

Influenza is a seasonally-epidemic viral infection causing 3-5 million severe illnesses and up to approximately 500,000 annual deaths around the world (Stohr 2002; Lee 2011). The elderly are more susceptible to influenza infection and complications, which was attributed to the phenomenon of immunosenescence or age-associated decline of immune system activity (Pop-Vicas and Gravenstein 2011; Talbot 2017). Diagnosis of influenza can't be made without virological confirmation, which is costly and rarely performed in public health surveillance systems. The World Health Organization (WHO) has recently revised the definition of ILI to be “acute respiratory illness with a measured temperature of  $\geq 38^{\circ}\text{C}$  and cough, with onset within the past 10 days” (Fitzner et al., 2017). Mounting effective innate immune response against influenza and other viral infections involve detection of viral infection by the intracellular foreign nucleic sensors Retinoic acid-inducible gene 1 (RIG-1) and Melanoma Differentiation-Associated protein 5 (MDA5) and induction of downstream antiviral proteins such as interferon-stimulated genes 15 (ISG15) and Myxoma Resistance Protein 1 (MX1) (Barral et al., 2009, Baum et al., 2010, Takeuchi and Akira 2010, Schoggins and Rice 2011).

In the current study, we test the hypothesis that Biobran/MGN-3 could reverse the decline of NK cell activity and improve resistance to influenza-like illnesses in older adults.

## **Rationale of the study**

Aging is associated with decline of NK cell activity, which renders geriatric population more susceptible to viral infection and malignancies. Biobran/MGN-3 dietary supplement was shown to increase NK cell activity in young adults and is expected to produce the same effect in geriatric population. Increase NK activity would increase resistance to viral infections and cancers in older adults.

## **Research questions**

1. Could Biobran/MGN-3 supplementation reduce the incidence of influenza-like illnesses in older adults?

2. Could Biobran/MGN-3 supplementation reduce the incidence density of influenza-like illnesses in older adults?
3. Does Biobran/MGN-3 supplementation increase NK cell activity in the geriatric population?
4. Does Biobran/MGN-3 supplementation upregulate expression of RIG-1, MDA5, ISG15, MX1?

## **Hypothesis**

Biobran/MGN-3 dietary supplements increases NK cell activity, upregulates RIG-1, MDA5, ISG15, MX1, and improves resistance to influenza-like illnesses in geriatric population.

## **Aim of the study**

To improve the quality of life together with reduction of health care costs among geriatric population via increasing immune system activity against infections and malignancy.

## **Specific objectives**

1. To assess the effect of daily dietary supplementation with Biobran/MGN-3 (500 mg/d for 3 months) on the incidence rate of influenza-like illnesses in older adults. The incidence rate will be calculated by dividing the number of incident ILI cases by the total number of the group participants.
2. To assess the effect of daily dietary supplementation with Biobran/MGN-3 (500 mg/d for 3 months) on the incidence density of influenza-like illnesses in older adults. The incidence density will be calculated by dividing the number of incident cases by the total person-time at risk.
3. To assess the effect of daily dietary supplementation with Biobran/MGN-3 (500 mg/d for 3 months) on NK number and activity in geriatric population. Activity of NK cells will be assessed using the degranulation assay.
4. To assess the effect of Biobran/MGN-3 (100 µg/ml for 72 h) on the pulmonary epithelial BEAS-2B cell lines expression levels of viral nucleic acid sensors Retinoic Acid-Inducible Gene 1 (RIG-1) and Melanoma Differentiation-Associated protein 5 (MDA5) as well as some of their downstream antiviral proteins Interferon-stimulated Genes 15 (ISG15), and Myxoma Resistance Gene 1 (MX1) using flow cytometry.

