### 3. Subjects:

Ninety apparently healthy older adults  $\geq 56$  years were originally recruited from the residents of Zagazig city visiting outpatient clinics at Zagazig University Hospitals. Only local residents were recruited so as to facilitate follow-up home visits and to reduce the dropout rate. Old age is associated with NK cell senescence. We recruited subjects  $\geq 56$  years of age in order to meet the WHO definition of old age in African nations (32). In addition, this age is close to public service retirement in Egyptian society, which is associated with significant social, mental, and psychological stress and therefore could be associated with significant decline in NK activity.

Males and females were randomly assigned into two groups (n=40/group) that received either placebo or Biobran/MGN-3 (500 mg/day for 3 months). Both the health care giver and the participants were blinded to the ingested supplement. Participants' health were monitored via weekly home visits and they were instructed to report any complaint or side effect by phone to the health care giver.

Diagnosis of ILI was made by documenting the incidence of acute respiratory illness with a measured temperature of  $\geq 38$  °C with cough (Fitzner et al., 2017). After diagnosis, the subject was helped to follow the proper health management

plan by the health care giver. During the study, all participants were required not to take any vitamins or medications during the study without consultation.

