### **2. Laboratory investigation:**

**Blood sampling, plasma and PBMCs isolation:** Study participants will be asked to donate blood samples (10 ml) at the start (basal) and at the termination of the study (4 weeks). Blood will be collected into heparinized tubes, diluted with an equal volume of DPBS (no  $\text{Ca}^{++}/\text{Mg}^{++}$ ), and peripheral mononuclear cells (PMBC) will be isolated by a standard Ficoll-Hypaque density gradient centrifugation method within 2h. Part of the plasma will be aspirated and frozen for analysis of liver and kidney functions. The lymphocyte band will be aspirated from the gradient interface, washed once with PBS supplanted with 1 mM EDTA and 0.1% BSA to remove platelets and once with a complete medium (CM; RPMI medium supplemented with 10% fetal bovine serum, 100-U/ml penicillin, 100 mg/ml streptomycin and 50 mg/ml gentamicin.), counted and assessed for viability in a trypan blue dye (0.2% (v/v) in PBS), and prepared as subsequently described for the different assays.

**Liver and kidney functions:** AST (serum glutamic oxaloacetic transaminase or SGOT), ALT (serum glutamic-pyruvic transaminase or SGPT), uric acid, creatinine will be assessed in plasma.

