### **3. Statistical analysis:**

Fisher's Exact test and OpenEpi, version 3.01, was used for comparing the incidence rates and the incidence density rates between groups. Mean  $\pm$  standard deviation is used to express continuous variables. Shapiro-Wilks test was used to determine the normality of data distribution. Two-tailed Student's t-test was used to compare Biobran/MGN-3 and placebo groups. Paired t-test was used to examine treatment effects within groups (i.e., comparisons of post-treatment versus pre-treatment).  $P \leq 0.05$  was considered statistically significant. SPSS version 20 was used for computing statistical analyses values.

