### **2. Consent:**

Informed consent will be obtained from all subject after explaining all study details, assuring confidentiality, and assuring their right of withdrawal at any time.

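### The ILI incidence rule has no provision for incomplete follow-up: on its plain reading unobserved weeks count as ILI-free, so unequal dropout biases the comparison, modestly if dropout is unrelated to ILI

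*Combined protocol and SAP*

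**What the plan says.** Specific objectives defines two ILI measures. For objective 1: "The incidence rate will be calculated by dividing the number of incident ILI cases by the total number of the group participants". For objective 2: "The incidence density will be calculated by dividing the number of incident cases by the total person-time at risk".

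The Statistical analysis section states that Fisher's exact test and OpenEpi "was used for comparing the incidence rates and the incidence density rates between groups". It names no analysis set and no leading ILI measure. It gives no rule for when person-time ends and no sensitivity analysis for incomplete follow-up.

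Dropout is foreseen. Under Subjects, only local residents were recruited, "so as to facilitate follow-up home visits and to reduce the dropout rate". The Consent section speaks of "assuring their right of withdrawal at any time". Setting and Subjects describe weekly home visits and phone calls. They do not say whether these go on once a participant stops the supplement.

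The size of the denominator is also unsettled. Subjects reports ninety people recruited, and Sample size proposes enrolling 90 for the ILI question. Yet "Males and females were randomly assigned into two groups (n=40/group"), which makes 80. The other 10 are not accounted for.

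**The concern.** A proportion with everyone in the denominator needs everyone's outcome. A participant who leaves in week 2 without an ILI stays in the objective 1 denominator as a non-case for the rest of the season, although nobody knows whether an ILI followed. Objective 2 gives the same person no time after leaving. Other things equal, the arm that loses more people then shows the lower incidence, which can create a difference or hide one.

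If the phrase for the denominator means completers, the problem changes but does not go away. Withdrawn participants are excluded after randomisation, and the comparison is biased whenever leaving is related to ILI risk. The text does not settle which reading applies.

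The NK comparison has a related gap. Participants are to "donate blood samples (10 ml) at the start (basal) and at the termination of the study (4 weeks"), while supplementation lasts 3 months. Until that timing is reconciled, one cannot say which early leavers would miss the second sample.

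**Working it through.** **Inputs from the documents.** 40 per group (Subjects), or 90/2 = 45 per group if all 90 are randomised (Sample size). Significance at P ≤ 0.05 (Statistical analysis). Two-tailed testing is stated only for the t-test, so a two-sided Fisher test is assumed here. The plan gives no ILI rate, dropout rate or ILI power, so it has no figure of its own to reproduce.

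**Assumptions.** The true 3-month ILI risk p is between 10% and 50%, with constant hazard h = −ln(1 − p). A share d of an arm leaves at fraction f of follow-up, independently of ILI risk.

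**Step 1: objective 1 on its plain reading.** The expected incidence is (1 − d)p + d[1 − (1 − p)^f].

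Example with p = 0.30 in both arms and f = 0.5, so that 1 − 0.70^0.5 = 0.1633:
- Active, d = 0.20: 0.80 × 0.30 + 0.20 × 0.1633 = 0.2727.
- Placebo, d = 0.05: 0.95 × 0.30 + 0.05 × 0.1633 = 0.2932.
- Risk ratio 0.2727/0.2932 = 0.93, although there is no effect.

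If they leave at the start (f = 0), the ratio is 0.80/0.95 = 0.84 whatever p is.

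In one arm with p = 0.20 and 8 of 40 leaving mid-course, the expected incidence is [32 × 0.20 + 8 × (1 − 0.80^0.5)]/40 = 18.1% instead of 20.0%.

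**Step 2: objective 2.** Under a constant hazard, expected person-time to first ILI or departure is the expected number of cases divided by h. Cases over person-time therefore returns h in each arm, whatever d and f are. The rate ratio stays at 1.00 under no effect. For true risks of 15% and 30% it is ln(0.85)/ln(0.70) = 0.456.

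**Step 3: no true effect.** Risk ratios cover p from 10% to 50%. Fisher rejection is by exact enumeration at p = 30% with 40 per arm.

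| Dropout, active vs placebo | Time of leaving | Objective 1 risk ratio | Fisher rejection |
|---|---|---|---|
| none | – | 1.00 | 2.8% |
| 20% vs 5% | mid-course | 0.93–0.94 | 3.2% |
| 20% vs 5% | start | 0.84 | 4.5% |
| 30% vs 5% | mid-course | 0.88–0.89 | 3.8% |
| 30% vs 5% | start | 0.74 | 8.0% |

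At p = 50%, 30% vs 5% leaving at the start gives 15.3% rejection. Equal dropout of 10% per arm leaves the ratio at 1.00.

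**Step 4: true risks 15% active, 30% placebo, 40 per arm.**

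| Dropout, active vs placebo | Time of leaving | Objective 1 risk ratio (true 0.50) | Fisher power |
|---|---|---|---|
| none | – | 0.50 | 28.1% |
| 5% vs 20% | mid-course | 0.54 | 20.9% |
| 5% vs 20% | start | 0.59 | 13.7% |
| 5% vs 30% | mid-course | 0.57 | 17.2% |
| 5% vs 30% | start | 0.68 | 7.9% |

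Results with 45 per arm are similar.

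**The case against.** The case for leaving the plan alone has weight. Weekly visits and local recruitment should keep dropout low. Objective 2 already allows for unequal follow-up, and two measures with different denominators are not a contradiction. Sample size calls the ILI part a pilot. At mid-course dropout of 20% versus 5% and 30% risk, Fisher's conservatism keeps the false-positive rate at 3.2%. All of this limits the size of the problem. It does not supply the missing rule, because the plan still tests the objective 1 incidence between groups.

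Three stronger readings are tempting and are not supported:

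- *Nothing is collected once a participant stops the supplement.* The documents are silent. No section ends the visits at that point, and if they continue, only loss of contact or withdrawal of consent loses ILI data.
- *A participant who leaves because of an early ILI is lost as a case.* On the plain reading, an ILI diagnosed at a visit or after a phone report is already in the numerator. Only illness after last contact is missed.
- *One or two missed cases decide the Fisher test.* This can happen: with 40 per arm, 2 vs 10 cases gives p = 0.025, and 3 vs 10 gives 0.066. But those counts are chosen near the threshold, with the missed case in one arm only. One missed case in each arm (3 vs 11) gives 0.037, and 3 vs 12 gives 0.020. Under the 20% mid-course model, 8 leavers cost 8 × (0.20 − 0.1056) = 0.76 expected cases, so one missed case needs about 10 to 11 leavers. Fewer leavers would do so on average only if leaving were related to ILI, and the documents give no evidence of that.

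**Conclusion.** The point holds as a gap with a bias of stated direction. Objective 1 either scores unobserved weeks as ILI-free or, if completers are meant, drops people after randomisation. The plan neither chooses between these readings nor protects against the consequences.

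If dropout is unrelated to ILI, the distortion is modest: an expected risk ratio of about 0.93 to 0.94 under no effect with 20% versus 5% leaving mid-course, and 0.84 if they leave at the start. Larger distortion needs early and strongly unequal dropout, or dropout related to ILI risk. The latter cannot be sized from the documents. Every ILI and dropout rate here is an assumption, and the figures use the plain reading with 40 per arm. The point deserves correction, but it does not show that the ILI result will be wrong.

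**What to change.** 1. In Specific objectives and Subjects, define the denominator as all randomised participants, analysed in their assigned arm, and reconcile 90 with 40 per group.
2. State that stopping the supplement is not leaving the study. Continue the already planned weekly visits or calls for ILI, and the planned final blood sample, in everyone who has not withdrawn consent. The documents must first reconcile whether that sample falls at 4 weeks or at the end of 3 months.
3. Estimate objective 1 as first-ILI cumulative incidence by Kaplan-Meier at a stated end of follow-up, censored at last contact. End person-time in objective 2 at the same point.
4. Report the number with incomplete follow-up, and its timing, by arm.
5. Add a sensitivity analysis for the unobserved weeks. Censoring is valid only if withdrawal is unrelated to ILI risk, so Kaplan-Meier alone does not repair informative dropout. Counting every incomplete participant as a case can serve as one bound, but not as the main result, because it penalises the arm with more dropout.

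The cost is a few sentences, one more analysis and some extra contacts in those who stop the supplement. Including time off the supplement may dilute the estimated effect.

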# Subject and Methods

## A) Technical design

### 1. study design:

Double-blind, placebo-controlled clinical trial. The study will span the time period from November 2018 till the end of February 2019, a period with known peak incidence of ILI attacks (Reafy et al., 2016).

### 2. Setting:

Outpatient clinics, Zagazig University Hospitals, and follow-up at home with phone calls and visits.

### 3. Subjects:

Ninety apparently healthy older adults  $\geq 56$  years were originally recruited from the residents of Zagazig city visiting outpatient clinics at Zagazig University Hospitals. Only local residents were recruited so as to facilitate follow-up home visits and to reduce the dropout rate. Old age is associated with NK cell senescence. We recruited subjects  $\geq 56$  years of age in order to meet the WHO definition of old age in African nations (32). In addition, this age is close to public service retirement in Egyptian society, which is associated with significant social, mental, and psychological stress and therefore could be associated with significant decline in NK activity.

Males and females were randomly assigned into two groups (n=40/group) that received either placebo or Biobran/MGN-3 (500 mg/day for 3 months). Both the health care giver and the participants were blinded to the ingested supplement. Participants' health were monitored via weekly home visits and they were instructed to report any complaint or side effect by phone to the health care giver.

Diagnosis of ILI was made by documenting the incidence of acute respiratory illness with a measured temperature of  $\geq 38$  °C with cough (Fitzner et al., 2017). After diagnosis, the subject was helped to follow the proper health management

plan by the health care giver. During the study, all participants were required not to take any vitamins or medications during the study without consultation.

**Inclusion criteria:**

1. Ages of 56+ years
2. Both sexes will be included.
3. Willing to participate in the study and give a written consent.

**Exclusion criteria:**

1. Subjects who took influenza vaccine, cortisone, or any other immunosuppressive agents such as radiation or chemotherapy.
2. Diagnosed with infections or malignancies.
3. Presence of auto-immune disorders.
4. Pregnant and lactating ladies.
5. Marked portal hypertension, pancytopenia, renal, or kidney failure.
6. Presence of major psychological insult or under medication for psychological insult.
7. Presence of chronic infections such as TB or HBV.
8. Inability to give a written consent.

**Risk to subjects:**

Biobran/MGN-3 is a food supplement that is produced from rice bran. It is available over-the-counter in the United States, Europe, and Japan. Clinical studies with Biobran/MGN-3 at larger doses and longer durations than what will be used in the current study were shown to be completely safe (Ghoneum, 1998; McDermott, 2006). Therefore, the risk to the participating subjects is negligible.

**Sample size:**

Previous clinical trials demonstrated that daily intake of Biobran/MGN-3 in young adults at doses of 15 mg/kg/d (~1000 mg/d), which is around 2 folds of the dose (500 mg/d) used in the current study, and 30 mg/kg/d (~2000 mg/d) increased NK cells activity after one month by 2 folds and 5 folds, respectively (Ghoneum,

1998). Therefore, it is reasonable to propose that doses of 500, 1000, and 2000 mg/d are within the linear portion of the Biobran/MGN-3 dose response curve. Thus, it is expected that Biobran/MGN-3 at a dose of 500 mg/kg will yield an effect size of 0.8. A power analysis using this effect size for a repeated measure analysis of variance with two measurements was performed using G\*Power software package (version 3.1.9.2, Franz Faul, Germany). With the criterion of significance (alpha) set at 0.05, a sample size of 13 subjects per group (total of 39 subjects) results in a power of 0.80 to yield a statistically significant result regarding NK cell activity.

With regards to the preventive efficacy on influenza-like illnesses, we propose to enroll 90 subjects as a pilot study.

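### The NK sample size contradicts itself for a two-group trial (13 per group is 26, not 39), and the inputs that would show which figure is wrong are not given

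*Combined protocol and SAP*

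**What the plan says.** All of the power reasoning is in the Sample size section. From earlier dose-response data it expects that the supplement "will yield an effect size of 0.8". It then reports "A power analysis using this effect size for a repeated measure analysis of variance with two measurements", run in G*Power with alpha 0.05, and concludes that "a sample size of 13 subjects per group (total of 39 subjects) results in a power of 0.80" for NK cell activity. The influenza-like illness outcome has no power calculation: "we propose to enroll 90 subjects as a pilot study".

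The Subjects section describes two groups, placebo and active: "Males and females were randomly assigned into two groups (n=40/group"). That makes 80 participants, although the same section opens with "Ninety apparently healthy older adults".

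The Statistical analysis section lists no repeated-measures ANOVA. For continuous outcomes it gives "Two-tailed Student's t-test was used to compare Biobran/MGN-3 and placebo groups" and "Paired t-test was used to examine treatment effects within groups". It does not say whether the between-group test compares post-treatment values or changes from baseline.

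**The concern.** The sentence gives two sample sizes that disagree for a two-group trial. Because 39 is exactly three times 13, a third group may have been entered in the software or left over from another design. Equally, 39 may be a two-group total with a wrong per-group number, or 13 may be right and the total wrong. Deciding between these needs the calculation's inputs, and four of them are missing: the metric of the effect size, the ANOVA effect tested, the number of groups and the pre-post correlation.

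NK activity is the only endpoint that the plan sizes. As written, a reader cannot tell how many participants the NK comparison needs, or to which test the 0.80 belongs.

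**Working it through.** **Inputs stated in the plan.** Alpha 0.05, power 0.80, effect size 0.8, two measurements, 13 per group and a total of 39 (Sample size); two groups of 40 (Subjects); two-tailed t-test between groups (Statistical analysis).

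**Inputs assumed here, because the plan gives none of them.** f = 0.4 (d/2, if 0.8 is d) or f = 0.8; pre-post correlation rho.

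**Step 1: arithmetic.** 13 × 2 = 26; 13 × 3 = 39; 39 / 2 = 19.5, that is 19 and 20. No assumption is needed to see the conflict.

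**Step 2: trying to reproduce the stated 0.80.** Power comes from the noncentral F distribution with m = 2 measurements, N participants and k groups. The noncentrality is λ = f²·N·m / (1 + rho) for the between-group effect and λ = f²·N·m / (1 − rho) for group-by-time. Degrees of freedom are k − 1 and N − k.

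| Reading (f = 0.4) | λ | Power |
|---|---|---|
| 2 groups, N = 39, between, rho 0.5 | 0.16·39·2/1.5 = 8.32 | 0.802 |
| 2 groups, N = 38, between, rho 0.5 | 0.16·38·2/1.5 = 8.11 | 0.791 |
| 2 groups, N = 26, group-by-time, rho 0.05 | 0.16·26·2/0.95 = 8.76 | 0.810 |
| 3 groups of 13, between, rho 0.2 | 0.16·39·2/1.2 = 10.40 | 0.797 |

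Each candidate can be brought to about 0.80 by a different choice of unstated inputs, so the stated power does not identify the slip. The choices matter a great deal. With two groups and N = 26 at f = 0.4, the between effect falls from 0.790 (rho 0) to 0.618 (rho 0.5) and 0.519 (rho 0.9), while group-by-time rises to 0.974 at rho 0.5. With two groups, f of 0.4 or 0.8 and rho from 0 to 0.9, power runs from 0.52 to above 0.99 at N = 26, and from 0.70 to above 0.99 at N = 39.

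**Step 3: the test actually planned.** With two groups and two measurements, the group-by-time F equals the square of the two-sample t on change, so naming an ANOVA in one place and a t-test in the other may be only a formal difference. What matters is which value the t-test analyses.

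*If 0.8 is d for the analysed value.* Noncentral t, two-sided 0.05, noncentrality δ = d·√(n₁n₂/(n₁+n₂)):

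| Per group | δ | Power |
|---|---|---|
| 13 / 13 | 0.8·√6.5 = 2.04 | 0.499 |
| 19 / 20 | 0.8·√(380/39) = 2.50 | 0.682 |
| 25 / 25 | 0.8·√12.5 = 2.83 | 0.791 |
| 26 / 26 | 0.8·√13 = 2.88 | 0.807 |
| 40 / 40 | 0.8·√20 = 3.58 | 0.942 |
| 45 / 45 | 0.8·√22.5 = 3.79 | 0.964 |

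Neither stated figure gives 0.80; the minimum is 26 per group, or 52 in total.

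*If 0.8 is f* (d = 1.6): δ = 1.6·√6.5 = 4.08 and power is 0.974 at 13 per group, so 13 is more than 0.80 requires.

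*If 0.8 is a difference in post-treatment SD units but change is analysed:* the effective d is 0.8/√(2(1 − rho)). At 40 per group, rho 0 gives d = 0.566 and power 0.705; rho 0.2 gives d = 0.632 and power 0.798; rho 0.5 gives d = 0.8 and power 0.942. Power reaches 0.80 at rho of about 0.205 with 40 per group, and at about 0.103 with 45.

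**The case against.** The strongest reply is that nothing turns on the slip. Enrolment of 80 or 90 exceeds 26, 39 and 52, the 90 is justified separately as a pilot for influenza-like illness, and the power at 40 per group is 0.94 if 0.8 is d for the analysed value. That stands and limits the severity. It also stands that the plan mentions no NK subset: the Laboratory investigation section asks study participants in general to give blood.

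A second reply is that the matches to 0.80 are found by choosing rho separately for each reading. Three groups of 13 give 0.868 at rho 0 and 0.697 at rho 0.5, and a total of 39 cannot be split equally (the smallest balanced total under that reading is 40, power 0.812). This is fair: the matches favour no reading, and they show only that the missing inputs decide the answer. That 39 = 3 × 13 is suggestive, but it does not show whether the calculation used three groups or one number was misreported.

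A third is that the gap between post-treatment value and change, and the gap between 80 and 90, are separate matters. They are distinct from the 13/39 slip, but a corrected power sentence cannot be written without settling both.

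**Conclusion.** The concern holds. That 13 per group and a total of 39 are incompatible in a two-group trial is certain and rests on no assumption. That the slip cannot be identified also holds, because the plan omits the effect-size metric, the effect tested, the number of groups and the correlation.

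The discrepancy is 26 against 39 in total, or 13 against 19 to 20 per group. For the planned t-test, on the assumption that 0.8 is d for the analysed value, the power is 0.50 or 0.68 instead of 0.80. The f and rho values used in the check are assumptions.

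This does not show that the trial is underpowered for NK activity: with all 80 or 90 participants assayed, power exceeds 0.80 under most readings. The exception is an analysis of change with a 0.8 SD post-treatment difference and a low correlation (0.70 at 40 per group and rho 0). It should be fixed because it is the plan's only power justification.

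**What to change.** 1. In Sample size, report the G*Power inputs actually used (d or f, effect tested, number of groups, rho) and correct the per-group and total numbers so that they agree for two groups.

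2. Restate the power for the between-group t-test in Statistical analysis, naming the effect-size metric and whether post-treatment values or changes are compared. A possible wording, to be used only if the authors confirm its assumption: *Assuming that 0.8 is Cohen's d for post-treatment NK activity, a two-sided two-sample t-test at alpha 0.05 has power 0.81 with 26 per group (52 in total) and 0.94 with 40 per group.* If change is analysed and 0.8 is a post-treatment SD difference, state the assumed rho and the power that follows from it.

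3. Reconcile 40 per group (80) with the 90 in Subjects and Sample size before entering the final number. At 45 per group, the power in the wording above becomes 0.96.

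4. Confirm in Laboratory investigation that NK activity is assayed in all randomised participants. If it is not, give the subset's size and power.

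The cost is wording only if everyone is assayed. A subset of 13 per group would have power 0.50 at d = 0.8. If change is analysed with a 0.8 SD post-treatment difference, 40 per group reaches 0.80 only when rho is at least about 0.2, and 45 per group when it is at least about 0.1.
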